### 8.2 Dose modifications for pembrolizumab based on adverse events during a cycle

CTCAE System/Organ/Class (SOC)	Adverse Event	Omit Treatment for Grade	Timing for Restarting Treatment	Treatment Discontinuation
Endocrine disorders	Endocrine disorders – Other, specify: Hypophysitis	2-4	AE resolves to Grade 0-1. Therapy with pembrolizumab can be continued while endocrine replacement therapy is instituted	AE does not resolve within 12 weeks of last dose or inability to reduce corticosteroid to 10 mg or less of prednisone or equivalent per day within 12 weeks
Endocrine disorders	Hyperthyroidism	3	AE resolves to Grade 0-1	AE does not resolve within 12 weeks of last dose or inability to reduce corticosteroid to 10 mg or less of prednisone or equivalent per day within 12 weeks
		4	Permanently discontinue	Permanently discontinue
Endocrine disorders	Hypothyroidism	2	Therapy with pembrolizumab can be continued while thyroid replacement therapy is instituted	Therapy with pembrolizumab can be continued while thyroid replacement therapy is instituted
Gastrointestinal disorders	Diarrhea or Colitis	2-3	AE resolves to Grade 0-1	AE does not resolve within 12 weeks of last dose or inability to reduce corticosteroid to 10 mg or less of prednisone or equivalent per day within 12 weeks
		4	Permanently discontinue	Permanently discontinue
General disorders and administration site conditions	Infusion related reaction	2 b	AE resolves to Grade 0-1	Permanently discontinue if AE develops despite adequate premedication
		3-4	Permanently discontinue	Permanently discontinue
Investigations	Aspartate aminotransferase (AST) increased or Alanine aminotransferase (ALT) increased or Blood bilirubin increased	2	AE resolves to Grade 0-1	AE does not resolve within 12 weeks of last dose
		3-4	Permanently discontinue (see exception below) a	Permanently discontinue
Metabolism and nutrition disorders	Glucose intolerance (Type 1 diabetes mellitus [if new onset]) or Hyperglycemia	3-4	Omit pembrolizumab for new onset Type 1 diabetes mellitus or Grade 3-4 hyperglycemia associated with evidence of beta cell failure	Resume pembrolizumab when patients are clinically and metabolically stable

CTCAE System/Organ/Class (SOC)	Adverse Event	Omit Treatment for Grade	Timing for Restarting Treatment	Treatment Discontinuation
Renal and urinary disorders	Acute kidney injury or Chronic kidney disease (e.g., Renal failure or Nephritis)	2	AE resolves to Grade 0-1	AE does not resolve within 12 weeks of last dose or inability to reduce corticosteroid to 10 mg or less of prednisone or equivalent per day within 12 weeks
		3-4	Permanently discontinue	Permanently discontinue
Respiratory, thoracic and mediastinal disorders	Pneumonitis	2	Hold pembrolizumab until AE resolves to Grade 0-1	AE does not resolve within 12 weeks of last dose or inability to reduce corticosteroid to 10 mg or less of prednisone or equivalent per day within 12 weeks
		3-4 or Recurrent 2	Permanently discontinue	Permanently discontinue
Cardiac disorders	Myocarditis	1-2	Hold pembrolizumab until AE resolves to Grade 0-1	Based on severity of AE administer corticosteroids
		3-4	Permanently discontinue	Permanently discontinue
	All Other Drug-Related Adverse Events c	3	AE resolves to Grade 0-1	AE does not resolve within 12 weeks of last dose or inability to reduce corticosteroid to 10 mg or less of prednisone or equivalent per day within 12 weeks
		4	Permanently discontinue	Permanently discontinue

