### 8.11 Instruction for initiation of a new cycle of therapy

A new cycle of treatment may begin on the scheduled Day 1 of a new cycle if:

- The ANC is  $\geq 1000/\mu\text{L}$
- The platelet count is  $\geq 75,000/\mu\text{L}$
- Any other non-hematologic drug-related (possible, probable, or definite) adverse event that may have occurred has resolved to  $\leq$ Grade 1 or baseline severity.

If these conditions are not met on Day 1 of a new cycle, dosing should be delayed for 1 week. At the end of that time, the patient should be re-evaluated to determine whether the criteria have been met. If the patient continues to fail to meet the above-cited criteria, delay therapy and continue to re-evaluate.

If any drug dosing was halted during the previous cycle and was restarted with a one-level dose reduction without requiring an interruption for the remainder of the cycle, then that reduced dose level will be initiated on Day 1 of the new cycle.

If any drug dosing was omitted for the remainder of the previous cycle or if the new cycle is held due to known hematologic toxicity newly encountered on the scheduled Day 1, then the new cycle will be started with a one-level dose reduction. If a new cycle of therapy cannot be restarted within 4 weeks of the scheduled Day 1 due to non-resolution of drug related toxicities, the patient will be removed from protocol therapy and will go to event monitoring.

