**Note: Permanently discontinue for any severe or Grade 3 drug-related AE that recurs or any life-threatening event.**

a For patients with liver metastasis who begin treatment with Grade 2 AST or ALT, if AST or ALT increases by greater than or equal to 50% relative to baseline and lasts for at least 1 week then patients should be discontinued.

b If symptoms resolve within one hour of stopping drug infusion, the infusion may be restarted at 50% of the original infusion rate (e.g., from 100 mL/hr to 50 mL/hr). Otherwise dosing will be held until symptoms resolve and the subject should be premedicated for the next scheduled dose.

c Patients with intolerable or persistent Grade 2 drug-related AE may hold study medication at physician discretion. Permanently discontinue study drug for persistent Grade 2 adverse reactions for which treatment with study drug has been held, that do not recover to Grade 0-1 within 12 weeks of the last dose.

\* Located at [REDACTED]

\*\* Use the following to describe actions in the Action column:

- Omit = The current dose(s) for the specified drug(s) during a cycle is skipped. The patient does not make up the omitted dose(s) at a later time
- Hold/Delay = The current dose(s) of all drugs during a cycle is delayed. The patient does make up the delayed dose(s) when the patient meets the protocol criteria to restart drugs.
- Discontinue = The specified drug(s) are totally stopped.

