### 8.3 Dose modifications for Ixazomib based on adverse events during a cycle

CTCAE System/Organ/Class (SOC)*	ADVERSE EVENT	ACTION**
Investigations	Neutrophil count decreased $<1.0 \times 10^9/L$ or Neutrophil count decreased $>1.0 \times 10^9/L$ (up to LLN) and Fever (temperature $>38.5^{\circ}C$ ) or Platelet count decreased $<30 \times 10^9/L$	Days 2-84: Ixazomib dose should be omitted on Days 1, 8, 15, 29, 36, 43, 57, 64, 71 as applicable Complete blood count (CBC) with differential should be followed weekly If ANC is $\geq 1.0 \times 10^9/L$ and/or platelet counts $\geq 30 \times 10^9/L$ , ixazomib may be reinitiated with 1 dose level reduction. The subsequent cycle will use the reduced dose.
Nervous System Disorders	Newly developed peripheral sensory neuropathy Grade 1 with pain or Peripheral sensory neuropathy Grade 2	Omit until resolution to Grade $<1$ or baseline No dose reduction necessary for this grade
	Peripheral sensory neuropathy with pain Grade 2 or Peripheral sensory neuropathy Grade 3	Omit ixazomib until toxicity resolves or returns to baseline. When toxicity resolves, re-initiate ixazomib at the next lower dose level.
	Peripheral sensory neuropathy Grade 4	Discontinue ixazomib. Peripheral neuropathy should be monitored until toxicity resolves or returns to baseline.
Skin and subcutaneous tissue disorders	Rash, maculo-papular, $\geq$ Grade 2	Omit ixazomib until rash resolves to $\leq$ Grade 1 (See Section 9.9a ). Restart at same dose. If the rash recurs, reduce dose by one dose level.
	Any other skin AE, Grade 4	Discontinue ixazomib and remove patient from all study treatment
	Any other Grade 3 attributable adverse event except: 
 
• Nausea and/or Vomiting Grade 3 in the absence of optimal anti-emetic prophylaxis
 
• Diarrhea Grade 3 that occurs in the absence of optimal supportive therapy
 
• Fatigue Grade 3
 
• Anemia
 
• White blood cell decreased
 
• Lymphocyte count decreased
 
	Omit ixazomib depending on the attribution, until resolution to Grade $\leq 1$ or baseline Restart at next lower dose. If a patient is already at the lowest drug level, go to event monitoring
	Any other Adverse Events Grade 4	Consider permanently discontinuing ixazomib – Exception if the investigator determines the patient is obtaining a clinical benefit

\* Located at [REDACTED]

\*\* Use the following to describe actions in the Action column:

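### The myocarditis row of Table 8.2 contradicts itself at Grade 1 and gives no limit for persistent Grade 1 disease or failure to taper steroids

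*Combined protocol and SAP*

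**What the plan says.** Table 8.2 in Section 8.2 has one column for the grade at which pembrolizumab is omitted, one for when it may restart, and one for when it is discontinued. For myocarditis of Grade 1-2 the restart cell reads "Hold pembrolizumab until AE resolves to Grade 0-1" and the discontinuation cell reads "Based on severity of AE administer corticosteroids". Grade 3-4 myocarditis means permanent discontinuation.

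Six other rows use the discontinuation column for a two-part limit: "AE does not resolve within 12 weeks of last dose or inability to reduce corticosteroid to 10 mg or less of prednisone" or its equivalent, the taper also to be achieved within 12 weeks.

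Four other places bear on the point:

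- **Section 8.11, Day 1 test.** A new cycle may start when "Any other non-hematologic drug-related (possible, probable, or definite) adverse event that may have occurred has resolved to" Grade 1 or lower, or to baseline.
- **Section 8.11, four-week rule.** Protocol therapy ends if a new cycle "cannot be restarted within 4 weeks of the scheduled Day 1 due to non-resolution of drug related toxicities".
- **Footnote c to Table 8.2.** "Permanently discontinue study drug for persistent Grade 2 adverse reactions for which treatment with study drug has been held" and not recovered to Grade 0-1 within 12 weeks of the last dose. The footnote marker sits on the row for all other drug-related events.
- **Section 9.9h.** It gives management advice for immune-related events and has no myocarditis entry.

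**The concern.** A dosing table should give one answer for each grade of an event. Here Grade 1 myocarditis appears in the column that says to withhold and also satisfies the cell that says when to resume. Two sites could read the row differently and both claim to follow it. One would withhold until the event clears. The other would give the next infusion with Grade 1 myocarditis still present.

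The second gap is the missing limit. For pneumonitis, colitis, nephritis and hypophysitis the table says when a slow recovery or a failed steroid taper ends pembrolizumab. For Grade 1-2 myocarditis, which the row itself says to treat with steroids according to severity, it does not. Yet Section 15.299c treats possible myocarditis as urgent: patients are told to report cardiac or breathing symptoms at once or seek emergency care.

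What is at stake is the safety of a rare patient and consistent handling across investigators. The efficacy inference is not affected.

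**Working it through.** **Step 1. Trigger against restart, row by row (Table 8.2).** Grades that go straight to permanent discontinuation are left out.

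| Event | Withheld at Grade | Restart at Grade | Overlap | Limit in discontinuation cell |
|---|---|---|---|---|
| Hypophysitis | 2-4 | 0-1 | no | 12 weeks + steroid taper |
| Hyperthyroidism | 3 | 0-1 | no | 12 weeks + steroid taper |
| Hypothyroidism | 2 | none; continue on replacement | n/a | none |
| Diarrhea or colitis | 2-3 | 0-1 | no | 12 weeks + steroid taper |
| Infusion reaction | 2 | 0-1 | no | own criterion |
| AST, ALT or bilirubin | 2 | 0-1 | no | 12 weeks only |
| Type 1 diabetes or hyperglycemia | 3-4 | none; resume when stable | n/a | none |
| Renal | 2 | 0-1 | no | 12 weeks + steroid taper |
| Pneumonitis | 2 | 0-1 | no | 12 weeks + steroid taper |
| **Myocarditis** | **1-2** | **0-1** | **Grade 1** | **none (steroid instruction)** |
| All other drug-related | 3 | 0-1 | no | 12 weeks + steroid taper |

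One row in 11 overlaps. By type of limit: 6 two-part, 1 with 12 weeks alone, 1 with its own criterion ("Permanently discontinue if AE develops despite adequate premedication"), 3 with none; 6 + 1 + 1 + 3 = 11. Of the three without a limit, hypothyroidism and glucose are handled by hormone replacement or metabolic control. Myocarditis is the only one of the three whose row calls for steroids.

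**Step 2. Does other text close the gap?**

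| Rule | Unresolved Grade 2 | Persistent Grade 1 | Cannot taper steroids |
|---|---|---|---|
| 8.11 Day 1 test | blocks a new cycle | passes | silent |
| 8.11 four-week rule | ends protocol therapy | not reached, because Grade 1 passes | silent |
| Footnote c | 12 weeks, if it applies to this row | silent | silent |
| Note below Table 8.2 | recurrent Grade 3, severe or life-threatening events only | silent | silent |
| 9.9h | no myocarditis entry | no entry | no entry |

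The 8.11 test applies on Day 1 of an 84-day cycle. For the Day 22, 43 and 64 infusions, Table 8.2 is the operative restart rule.

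**Step 3. Size.** Section 15.27 lists myocarditis at 0.1% to <1% for pembrolizumab. Assume that this range carries over to the combination. Section 16.12 gives 37 evaluable and at most 41 accrued patients.

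- Expected cases = n × p. For n = 37: 37 × 0.001 = 0.037 and 37 × 0.01 = 0.37. For n = 41: 0.041 and 0.41.
- Chance of at least one case = 1 − (1 − p)^n. For n = 37: 1 − 0.999^37 = 0.036 and 1 − 0.99^37 = 0.311. For n = 41: 0.040 and 0.338.

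These figures cover every grade. The Grade 1-2 share is smaller, and the documents do not give it.

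**Step 4. Doses at stake under a 12-week limit.** Infusions fall on Days 1, 22, 43 and 64, then Day 85 (Day 1 of the next 84-day cycle), so every 21 days. Scheduled doses before day 84 after the last dose fall at 21, 42 and 63 days: three doses.

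**The case against.** **The row can be read safely.** Grade 1 stands in the column for withholding, so an investigator who reads the whole row would withhold. This stands in part. A reader might infer that the protocol authorizes infusion during ongoing Grade 1 myocarditis. The documents do not support that as a plain reading: the row gives two incompatible answers. For a Grade 2 event falling to Grade 1, the restart cell points to re-dosing while the trigger column still points to withholding.

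**Myocarditis is not singled out across the protocol.** A reader might infer that it is the only event acted on at Grade 1. That is true of Table 8.2 only. Table 8.3 omits ixazomib for "Newly developed peripheral sensory neuropathy Grade 1 with pain", and Table 8.4 acts on Grade 1 dyspepsia, ulcer and gastritis.

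**The event is partly covered.** Grade 3-4 is permanently discontinued, the four-week rule catches Grade 2 that is unresolved at a new cycle, and footnote c may add 12 weeks. Pre-dose checks for immune-related events (Section 10.81) and investigator withdrawal (Section 13.5) also remain. It would therefore be wrong to say that nothing limits low-grade myocarditis. What remains open is persistent Grade 1 and failed taper, because the general safeguards set no restart grade and no taper limit.

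**The trigger may be the slip.** If Grade 2 was intended, the restart cell matches the pneumonitis row and the overlap disappears. The documents do not show which cell is wrong, nor do they say that re-dosing at Grade 1 is unsafe. This objection stands as to the cause. Either way the row needs correcting, and the missing limit is unaffected.

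**Conclusion.** The point holds as an internal contradiction in a safety dosing rule, together with a missing limit. Both facts can be read directly from Table 8.2, and no other section resolves persistent Grade 1 or inability to taper.

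The reach is small: fewer than about 0.4 expected cases of any grade in 37 to 41 patients, and at most roughly a one-in-three chance of seeing any. This rests on the listed pembrolizumab frequency applying to the three-drug regimen. The significance level, the power and the response decision rule are untouched. The reason to act is that the correction is cheap and the event is one the protocol treats as urgent.

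**What to change.** 1. **Restart cell, Grade 1-2.** Keep the verb (hold) and change only the grade: hold pembrolizumab until the event is at Grade 0 or back to baseline, and state that this also governs pembrolizumab on Day 1 of a new cycle. Table 8.3 is the model: its neuropathy row with a Grade 1 trigger requires resolution below Grade 1 or to baseline. Raising the trigger to Grade 2 would also remove the overlap, but it would give up the protocol's own stricter trigger.
2. **Discontinuation cell, Grade 1-2.** Insert the two-part limit from the six other rows: no resolution within 12 weeks of the last dose, or steroids not reduced to 10 mg prednisone or equivalent per day within 12 weeks.
3. **Section 9.9h.** Add a myocarditis entry and move the corticosteroid instruction there.
4. **Meaning of hold.** The definitions under Table 8.2 make a hold a delay of all drugs with doses made up later, and an omission a skip of the named drug only. The column heading says omit and the cell says hold. The sponsor should state which is meant, and the edit should not loosen any existing all-drug delay.

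**Cost.** Two cells and one added entry. If only pembrolizumab is withheld, a rare patient with persistent Grade 1 myocarditis misses up to three infusions and stops pembrolizumab at 12 weeks. Ixazomib and dexamethasone could then continue, since the note in Section 8.1 ends all treatment only when ixazomib stops. A patient who recovers in time may have to restart at the reduced schedule of Days 1 and 43 (Section 8.1, level -1) if Section 8.11 counts the doses as omitted for the rest of a cycle. If hold means all drugs, the stricter restart grade also lengthens the delay of ixazomib and dexamethasone.

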**Note: Permanently discontinue for any severe or Grade 3 drug-related AE that recurs or any life-threatening event.**

a For patients with liver metastasis who begin treatment with Grade 2 AST or ALT, if AST or ALT increases by greater than or equal to 50% relative to baseline and lasts for at least 1 week then patients should be discontinued.

b If symptoms resolve within one hour of stopping drug infusion, the infusion may be restarted at 50% of the original infusion rate (e.g., from 100 mL/hr to 50 mL/hr). Otherwise dosing will be held until symptoms resolve and the subject should be premedicated for the next scheduled dose.

c Patients with intolerable or persistent Grade 2 drug-related AE may hold study medication at physician discretion. Permanently discontinue study drug for persistent Grade 2 adverse reactions for which treatment with study drug has been held, that do not recover to Grade 0-1 within 12 weeks of the last dose.

\* Located at [REDACTED]

\*\* Use the following to describe actions in the Action column:

- Omit = The current dose(s) for the specified drug(s) during a cycle is skipped. The patient does not make up the omitted dose(s) at a later time
- Hold/Delay = The current dose(s) of all drugs during a cycle is delayed. The patient does make up the delayed dose(s) when the patient meets the protocol criteria to restart drugs.
- Discontinue = The specified drug(s) are totally stopped.

### 8.3 Dose modifications for Ixazomib based on adverse events during a cycle

CTCAE System/Organ/Class (SOC)*	ADVERSE EVENT	ACTION**
Investigations	Neutrophil count decreased $<1.0 \times 10^9/L$ or Neutrophil count decreased $>1.0 \times 10^9/L$ (up to LLN) and Fever (temperature $>38.5^{\circ}C$ ) or Platelet count decreased $<30 \times 10^9/L$	Days 2-84: Ixazomib dose should be omitted on Days 1, 8, 15, 29, 36, 43, 57, 64, 71 as applicable Complete blood count (CBC) with differential should be followed weekly If ANC is $\geq 1.0 \times 10^9/L$ and/or platelet counts $\geq 30 \times 10^9/L$ , ixazomib may be reinitiated with 1 dose level reduction. The subsequent cycle will use the reduced dose.
Nervous System Disorders	Newly developed peripheral sensory neuropathy Grade 1 with pain or Peripheral sensory neuropathy Grade 2	Omit until resolution to Grade $<1$ or baseline No dose reduction necessary for this grade
	Peripheral sensory neuropathy with pain Grade 2 or Peripheral sensory neuropathy Grade 3	Omit ixazomib until toxicity resolves or returns to baseline. When toxicity resolves, re-initiate ixazomib at the next lower dose level.
	Peripheral sensory neuropathy Grade 4	Discontinue ixazomib. Peripheral neuropathy should be monitored until toxicity resolves or returns to baseline.
Skin and subcutaneous tissue disorders	Rash, maculo-papular, $\geq$ Grade 2	Omit ixazomib until rash resolves to $\leq$ Grade 1 (See Section 9.9a ). Restart at same dose. If the rash recurs, reduce dose by one dose level.
	Any other skin AE, Grade 4	Discontinue ixazomib and remove patient from all study treatment
	Any other Grade 3 attributable adverse event except: 
 
• Nausea and/or Vomiting Grade 3 in the absence of optimal anti-emetic prophylaxis
 
• Diarrhea Grade 3 that occurs in the absence of optimal supportive therapy
 
• Fatigue Grade 3
 
• Anemia
 
• White blood cell decreased
 
• Lymphocyte count decreased
 
	Omit ixazomib depending on the attribution, until resolution to Grade $\leq 1$ or baseline Restart at next lower dose. If a patient is already at the lowest drug level, go to event monitoring
	Any other Adverse Events Grade 4	Consider permanently discontinuing ixazomib – Exception if the investigator determines the patient is obtaining a clinical benefit

\* Located at [REDACTED]

\*\* Use the following to describe actions in the Action column:

- Omit = The current dose(s) for the specified drug(s) during a cycle is skipped. The patient does not make up the omitted dose(s) at a later time
- Hold/Delay = The current dose(s) of all drugs during a cycle is delayed. The patient does make up the delayed dose(s) when the patient meets the protocol criteria to restart drugs.
- Discontinue = The specified drug(s) are totally stopped.

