#### 9.9b Thrombocytopenia

Blood counts should be monitored regularly as outlined in the protocol with additional testing obtained according to standard clinical practice. Thrombocytopenia may be severe but has been manageable with platelet transfusions according to standard clinical practice. Ixazomib administration should be modified as noted as per dose modification recommendations in the protocol when thrombocytopenia occurs (see Section 8). Therapy can be reinitiated at a reduced level upon recovery of platelet counts. A rare risk is thrombotic thrombocytopenic purpura (TTP), a rare blood disorder where blood clots form in small blood vessels throughout the body characterized by thrombocytopenia, petechiae, fever, or possibly more serious signs and symptoms. TTP should be managed symptomatically according to standard medical practice.

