#### 9.9c Neutropenia

Blood counts should be monitored regularly as outlined in the protocol section 4.0 with additional testing obtained according to standard clinical practice. Neutropenia may be severe but has been manageable. Growth factor support is not required but may be considered according to standard clinical practice. Ixazomib administration should be modified as noted as per dose modification recommendations in the protocol when neutropenia occurs (see Section 8). Therapy can be reinitiated at a reduced level upon recovery of ANCs.

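### In the low-count row of Table 8.3, the ixazomib restart clause is inconsistent with the omission triggers beside it: read as an inclusive OR, it can be met while the reason for the omission persists

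*Combined protocol and SAP*

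**What the plan says.** The low-count row of Table 8.3 (Section 8.3) lists three omission criteria joined by 'or'. It begins "Neutrophil count decreased $<1.0 \times 10^9/L$ or Neutrophil count decreased" and continues with the febrile band (ANC above 1.0 up to LLN, with temperature above 38.5 °C) and then platelets below 30. Any one is enough. The action, headed Days 2-84, is "Ixazomib dose should be omitted on Days 1, 8, 15, 29, 36, 43, 57, 64, 71 as applicable", and "Complete blood count (CBC) with differential should be followed weekly". Restart is allowed if ANC is at least 1.0 "and/or platelet counts $\geq 30 \times 10^9/L$ , ixazomib may be reinitiated with 1 dose level reduction".

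Three other places bear on restart:

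- Section 9.9b: "Therapy can be reinitiated at a reduced level upon recovery of platelet counts".
- Section 9.9c: "Therapy can be reinitiated at a reduced level upon recovery of ANCs".
- Section 8.11 requires ANC of at least 1000/µL and platelets of at least 75,000/µL together, but only to begin a new cycle: "If these conditions are not met on Day 1 of a new cycle, dosing should be delayed for 1 week".

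The footnote to Table 8.3 defines omission dose by dose: the current dose is skipped and not made up.

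**The concern.** Dosing stops when any one criterion is present, so restart should require that none is. The logical complement of an 'or' of triggers is an 'and' of recoveries. An inclusive 'and/or' asks for less, since one adequate count satisfies it even if the other count caused the omission and has not moved. The fever criterion is affected in a different way. It applies only when ANC is above 1.0, so a patient omitted for it already meets the ANC half of the restart clause.

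What is at stake is the clarity of a dosing instruction that governs most of each cycle. Ixazomib is given on nine days of an 84-day cycle (Section 7.1). Section 8.11 covers Day 1, and the other eight dosing days fall under Table 8.3. That cell is the only place with numerical mid-cycle restart thresholds for low counts. The neuropathy, maculo-papular rash and other-Grade-3 rows of the table tie restart to resolution of the event that caused the omission. This row does not do so in terms.

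**Working it through.** The plan gives no figure on this point, so the check is of the logic of the rule. All thresholds come from the low-count row of Table 8.3, with counts in ×10⁹/L.

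**Rules compared**

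- Omit: ANC <1.0, OR (ANC >1.0 up to LLN AND temperature >38.5 °C), OR platelets <30.
- Restart, inclusive reading: ANC ≥1.0 OR platelets ≥30.
- Restart, plain AND: ANC ≥1.0 AND platelets ≥30.
- Restart, proposed: plain AND, plus temperature ≤38.5 °C if ANC is below LLN.

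**Step 1: worked cases, counts only**

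| ANC | Platelets | Count trigger present | Inclusive reading | Plain AND |
|---|---|---|---|---|
| 0.6 | 20 | both | not met | not met |
| 0.6 | 90 | ANC | met (90 ≥ 30) | not met |
| 1.3 | 20 | platelets | met (1.3 ≥ 1.0) | not met |
| 1.3 | 90 | none | met | met |

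Of the 3 combinations with a low count, the inclusive reading is met in 2 and plain AND in 0.

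**Step 2: add the fever criterion**

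Three ANC bands × two platelet bands × fever yes or no = 12 combinations.

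| ANC band | Platelets | Temp >38.5 °C | Combinations | Trigger | Inclusive | Plain AND | Proposed |
|---|---|---|---|---|---|---|---|
| <1.0 | <30 | either | 2 | yes | no | no | no |
| <1.0 | ≥30 | either | 2 | yes | yes | no | no |
| >1.0 to LLN | <30 | either | 2 | yes | yes | no | no |
| >1.0 to LLN | ≥30 | yes | 1 | yes | yes | yes | no |
| >1.0 to LLN | ≥30 | no | 1 | no | yes | yes | yes |
| above LLN | <30 | either | 2 | yes | yes | no | no |
| above LLN | ≥30 | either | 2 | no | yes | yes | yes |

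- Trigger present: 2 + 2 + 2 + 1 + 2 = 9. Trigger absent: 1 + 2 = 3.
- Of the 9, restart is met in 2 + 2 + 1 + 2 = 7 on the inclusive reading, in 1 with plain AND, and in 0 with the proposed wording.
- Of the 3 with no trigger, the proposed wording allows restart in all 3.

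Replacing 'and/or' by 'and' would therefore repair the count problem but leave the febrile case open.

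**Step 3: boundary**

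The febrile band starts above 1.0, so ANC of exactly 1.0 with fever is not a trigger today. The grid has no cell for it. The proposed wording would hold restart there, because 1.0 lies below LLN (the row's own band runs from 1.0 up to LLN).

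**The case against.** The strongest reply is that the restart sentence should not be read alone. The omission instruction in the same cell is a directive ('should'), lists every dosing day, and rests on a per-dose definition of omission. With platelets of 20 it applies again on the next dosing day, and a permissive 'may' does not cancel it. 'And/or' can also be read distributively: ANC must recover if ANC was low, platelets if platelets were low, both if both were. That reading agrees with Sections 9.9b and 9.9c. Section 8.11 separately requires both counts, with a higher platelet threshold, at each new cycle.

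Much of this stands. A reader might infer that the protocol authorises dosing at a count below threshold, or that Table 8.3 contradicts Sections 9.9b and 9.9c. The documents support neither inference: the directive still applies, and a natural reading makes the sections agree.

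Three gaps remain. The distributive reading is not written down. Sections 9.9b and 9.9c give no threshold and send the reader back to Section 8, while Section 8.11 is silent after Day 1. The distributive reading also does not help the febrile case, since the ANC condition is already met when the dose is omitted and no restart text mentions temperature.

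**Conclusion.** The point holds as an internal inconsistency in one row of a safety table. On an inclusive reading, the restart clause is met in 7 of the 9 trigger combinations, including the febrile one, where it is met from the start. The intended meaning, that the affected count must recover, can be reconstructed from the omission directive and Sections 9.9b and 9.9c. This is therefore a wording error, and it does not show that anyone intended dosing at low counts.

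The result assumes only that 'and/or' is read inclusively and the clause is read by itself. The 7 of 9 counts combinations of conditions. It is not a share of patients or doses, nor a measure of risk. A reader might be tempted to attach a frequency from the 43% drug-related thrombocytopenia reported for single-agent ixazomib in Section 1.4. That figure is given without grade, and the documents give no rate for platelets below 30, so no frequency or harm estimate follows. The response endpoint definition, sample size, significance level and power are unaffected.

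**What to change.** Replace the restart condition in the low-count row of Table 8.3 with wording to this effect:

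> When none of the omission criteria in this row is present (ANC ≥1.0 × 10⁹/L AND platelets ≥30 × 10⁹/L and, if ANC is below LLN, temperature ≤38.5 °C), ixazomib may restart one dose level lower.

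This uses only thresholds already in the row. Any stricter rule on resolution of fever is a clinical choice for the sponsor.

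The cost is one clause in one cell. No new test is needed, because the row already asks for weekly counts. Two small downsides should be acknowledged. ANC of exactly 1.0 with fever, not named as a trigger now, would also wait. Restart may also come slightly later for any patient who would have been managed on the looser reading.
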